**5.4 Permitted and prohibited treatment**

**5.4.1 Permitted treatment**

Patients with comorbidities may continue taking previously prescribed medications. Patients will be asked to report any medications and dietary supplements they were taking within a month prior to the screening or have taken during the study. The investigator will document any medication the patient is taking in the source documents and CRF.

Additionally, it is recommended to avoid nonsteroidal anti-inflammatory drugs, including selective cyclooxygenase-2 inhibitors, and ascorbic acid at a dose >3 g/day due to the increased risk renal function impairment.

#### **5.4.2 Prohibited treatment**

During the treatment with the investigated product, patients **should not take**:

- Other antihypertensive drugs, except for the investigated products. The only exception is short-acting antihypertensives prescribed by the investigator to relieve hypertensive episodes PRN. These medications should be withheld the day prior to the visit to avoid effects on blood pressure measurement during the visit and evaluation of the investigated treatment efficacy.
- Thiazide diuretics, corticosteroids, bisphosphonates or levothyroxine since these agents are known to affect bone metabolism and BMD.
- Antacids, if the interval between an antacid and the investigated product administration is less than 2 hours.

If there is a need to prescribe the prohibited treatment to a patient or it became known that a patient is receiving the prohibited treatment, the patient is withdrawn from the study.

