### **4.3 Exclusion criteria**

A patient must not meet any of the following exclusion criteria:

1. Hypersensitivity to moxonidine, bisoprolol or any other ingredient of the respective formulations
2. Any Contraindications for moxonidine, bisoprolol
3. Osteoporosis (T-score below - 2.5 SD).
4. Primary or secondary hyperparathyroidism.
5. Paget's disease of bones.
6. History of low traumatic bone fractures.
7. Malabsorption syndrome.
8. History of gastro-intestinal surgery.
9. Severe disturbance of peripheral circulation.
10. Raynaud's disease.
11. Symptomatic (secondary) hypertension (caused by any primary internal diseases)

12. Morbid obesity (BMI over 40 kg/m^2).
13. Symptoms of estrogen deficiency such as hot flushes, night sweats, vaginal dryness
14. Administration of any hormone-replacement therapy (HRT) or intake of isoflavones
15. Secondary hypogonadism.
16. Systolic BP  $\geq$ 180 mm Hg and/or Diastolic BP  $\geq$ 110 mm Hg.
17. Clinical presentations of cardiovascular disease: coronary heart disease (CHD), history of stroke, transient ischemic attack (TIA), Charcot's syndrome.
18. Severe heart failure.
19. Hemodynamically significant congenital heart disease.
20. Heart rhythm disorders which require permanent use of any antiarrhythmic medications (including  $\beta$ -adrenoblockers and calcium antagonists).
21. Diabetes mellitus of any genesis.
22. Severe liver failure.
23. Severe kidney failure including patients on dialysis
24. Thyroid diseases accompanied by functional disorders (thyrotoxicosis or uncompensated hypothyroidism).
25. Alcohol and drug abuse.
26. Patients with oncological diseases diagnosed within 5 years before IC execution.
27. Inability of the patient to comprehend the essence of the program and to provide his/her consent for participation in the program.
28. Patients with any condition, which in the opinion of the Investigator makes the patient unsuitable for inclusion based on clinical judgment.
29. Corticosteroid therapy
30. Participation in any other clinical study during the whole course of this investigation including participation in a study within 30 days prior to providing the informed consent for this trial

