#### **4.4 Start of treatment criteria**

Start of investigated treatment (i.e., patient enrollment to the study) is possible when all of the following conditions are met during the enrollment visit:

1. Patient is to meet all the inclusion criteria and should lack any of the exclusion criteria.

2. Patients previously treated with antihypertensive agents have undergone 7-10-day washout period according to the protocol (all antihypertensive drugs are discontinued, except fast-acting agents to relieve hypertensive episodes).

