#### **4.5 Study withdrawal criteria**

A patient may be withdrawn from the study before the treatment is started, if the investigator discovers deviations from any inclusion criteria, exclusion criteria, or criteria for the treatment initiation. Patients who withdrew before the treatment start (i.e., during screening or washout period), will be substituted with new patients.

In the present study, withdrawal from the study will also mean discontinuation of the investigated treatment.

The patient may be withdrawn from the study due to the following reasons:

1. Withdrawal of the informed consent to participate in the study.
2. Low treatment compliance (<80%).
3. Adverse events that in the investigator's opinion make the treatment continuation impossible, dangerous, or inconsistent with best patient interest and safety. A SAE is not necessarily the cause of early patient withdrawal from the study.
4. According to the investigator, continued participation of the patient in the study threatens the patient's safety.
5. It is necessary to administer treatment prohibited by the study protocol.
6. Failure of the investigated treatment (i.e., recurrent rise of blood pressure  $\geq 180/120$  mmHg after previously achieved target BP level).
7. Death of the patient.
8. Sponsor decision.

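### Levothyroxine and bisphosphonates force withdrawal on study but are not barred at entry, so an eligible woman can be randomised and then removed for a drug already known at screening.

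*Combined protocol and SAP*

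**What the plan says.** Section 5.4.2 lists drugs that patients must not take during treatment. The bone-related entry reads "Thiazide diuretics, corticosteroids, bisphosphonates or levothyroxine since these agents are known to affect bone metabolism and BMD". The section ends with a mandatory consequence: if such a drug has to be prescribed, or "it became known that a patient is receiving the prohibited treatment, the patient is withdrawn from the study". Section 4.5 lists a related ground for withdrawal, "It is necessary to administer treatment prohibited by the study protocol", under wording that makes withdrawal possible rather than compulsory.

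The entry rules are in sections 4.2 to 4.4 and are repeated in the synopsis. Of the four classes in 5.4.2, the exclusion list names one: "29. Corticosteroid therapy". The thyroid exclusion, number 24, is limited to "Thyroid diseases accompanied by functional disorders (thyrotoxicosis or uncompensated hypothyroidism". Bisphosphonates appear in no criterion. Section 4.4 adds, for previously treated patients, a washout in which "all antihypertensive drugs are discontinued, except fast-acting agents to relieve hypertensive episodes".

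Section 5.4.1 says "Patients with comorbidities may continue taking previously prescribed medications". It does not refer to the prohibited list that follows it.

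Sections 6 and 10.3 place the efficacy analysis in patients who completed according to protocol. Section 10.2 says that patients who did not finish treatment are brought in by last observation carried forward. It also defines an ITT set, to which no efficacy analysis is assigned.

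**The concern.** A drug that disqualifies a patient from staying in the trial should be dealt with before she is randomised. Here two such drugs are recorded at screening but acted on, if at all, only after allocation. That turns a baseline characteristic into a post-randomisation exclusion.

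There are two ways for this to do harm. If the use is acted on, the patient is withdrawn, and under sections 6 and 10.3 she leaves the only population named for efficacy, including the primary CTX comparison. If it is overlooked, or if 5.4.1 is taken at face value, she stays in and her CTX and BMD changes reflect a drug that the protocol bars for its effect on exactly those measures. Section 1.1 criticises earlier beta-blocker studies for confounding of this kind, so the authors regard it as material.

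**Working it through.** **Step 1. Trace each barred class through the entry rules.**

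| Class in 5.4.2 | Barred by 4.3? | Stopped by 4.4? | Can an eligible user be randomised? |
|---|---|---|---|
| Corticosteroids | Yes, no. 29 | Not needed | No |
| Thiazides (as antihypertensives) | Not named | Yes, washout | No, if still taking them |
| Levothyroxine | Not named; no. 24 leaves compensated hypothyroidism eligible | No | Yes |
| Bisphosphonates | Not named; no. 3 excludes osteoporosis, not treatment of osteopenia | No | Yes |

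**Step 2. Follow a woman with compensated hypothyroidism on levothyroxine.** She meets 4.2, breaches nothing in 4.3 and satisfies 4.4. At V1 the envelope is opened and the first dose is taken at the same visit (3.6.2, 5.1). Section 5.4.1 tells her she may continue her prescription; 5.4.2 requires her withdrawal because of it. Both rules cannot be followed.

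**Step 3. Ask whether she is replaced.** Section 4.5 substitutes only patients who leave before treatment starts. Section 3.2 prepares 114 envelopes, 57 per arm. No provision covers a later loss.

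**Step 4. Ask whether she is analysed.** Under sections 6 and 10.3 she is not. Under section 10.2 she would be carried forward. However, CTX is scheduled only at V1, V3 (week 24) and V4 (week 48). A woman withdrawn before V3 has no scheduled on-treatment CTX to carry, and the ITT definition requires V3 or V4 data. Section 4.6 asks for final-visit procedures after early withdrawal, but only where possible.

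**Step 5. Size.** The plan's own figure comes first. Section 10.5 chooses 114 on feasibility: 300 screened at about 3 to 1 gives 300/3 = 100, the stated minimum, while 114 corresponds to 300/114 = 2.63 to 1. There is no effect size, SD, power or dropout figure, so no power calculation can be reproduced.

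The documents give no prevalence of levothyroxine or bisphosphonate use. Let *p* be the assumed proportion of the 114 who are affected and withdrawn, spread evenly over the arms, with no other losses:

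- number lost = 114*p*
- interval widening = √[1/(1 − *p*)] − 1
- difference detectable with 80% power, two-sided 0.05, in SD units = (1.960 + 0.842) × √[2/(57(1 − *p*))]
- chance of at least one affected patient = 1 − (1 − *p*)^114

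| *p* (assumed) | Lost | Left | Intervals wider by | Detectable difference | Chance of at least one |
|---|---|---|---|---|---|
| 0 | 0 | 114 | 0 | 0.525 SD | – |
| 2% | 2.3 | 111.7 | 1.0% | 0.530 SD | 90% |
| 5% | 5.7 | 108.3 | 2.6% | 0.538 SD | 99.7% |
| 10% | 11.4 | 102.6 | 5.4% | 0.553 SD | >99.9% |
| 15% | 17.1 | 96.9 | 8.5% | 0.569 SD | >99.9% |

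The detectable difference is a yardstick only, since the plan sets no target.

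**The case against.** The best reply is that the protocol already gives the investigator what is needed. Section 3.6.1 collects 30 days of medication history before randomisation. Section 5.4.1 requires every drug to be recorded. Exclusion 28 covers "Patients with any condition, which in the opinion of the Investigator makes the patient unsuitable for inclusion based on clinical judgment". A sensible reader would also let the specific ban in 5.4.2 qualify the general permission in 5.4.1. On that view, randomising such a woman is a lapse rather than the normal path.

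Part of this stands. An attentive investigator can keep these women out, and the table above counts every affected woman as missed at entry and later withdrawn, so each row is an upper limit for its assumed prevalence. But exclusion 28 is discretionary, no criterion applies the medication history to these drugs, and reading 5.4.2 as overriding 5.4.1 settles only whether she may stay in, not whether she may enter.

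It can also be said that the trial is exploratory with no power target, and that the loss of precision is small to moderate. That is correct. The objection to excluding patients after randomisation does not depend on a power target.

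Three stronger readings are tempting, and the documents do not support them. First, a reader might add thiazides, since no numbered exclusion names them. Section 4.4 makes stopping all antihypertensives a condition of enrolment, and section 5.1 keeps out patients who do not meet the washout conditions, so current users are dealt with before randomisation. Whether 7 to 10 days is long enough for baseline CTX is a different question and removes nobody from the analysis. Second, a reader might take loss from the primary analysis as settled; section 10.2 contradicts it. Third, because the trial is open-label, a reader might infer that use is detected more often in one arm. Medication is recorded in the same way in both arms, and the documents give no mechanism or direction for a difference.

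**Conclusion.** The point holds for levothyroxine and bisphosphonates. It is a contradiction between stated rules, not a missing detail: followed as written, sections 4.2 to 4.4 and 5.4.1 admit and keep a patient whom 5.4.2 removes. She is not replaced, and on the wording of sections 6 and 10.3 she leaves the efficacy population, subject to the unresolved conflict with section 10.2.

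The size is uncertain because prevalence is unknown. The range of 2 to 17 women, with intervals 1-8.5% wider, rests wholly on an assumed 2-15% and on every affected woman being randomised and then withdrawn. Precision is the lesser issue. The greater one is an avoidable exclusion after randomisation or, if use is missed, a bone-active drug left in the CTX and BMD comparison. No direction of bias between arms can be claimed. This should be corrected, but it does not by itself undermine the trial.

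**What to change.** Reconcile sections 4.3 and 4.4 (and the matching synopsis text) with 5.4.1 and 5.4.2, so that the rule for entering on levothyroxine or a bisphosphonate agrees with the rule for continuing on it. Whether existing users are excluded or allowed is for the sponsor to decide; the statistical need is only that the two rules match. State in 5.4.1 how it relates to 5.4.2.

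Add a line to the V0/V1 checklist requiring the reconciled rule to be confirmed from the 30-day medication history before the envelope is opened.

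Separately, say which of sections 10.2 and 10.3 governs patients who are withdrawn, since that decides whether any remaining case is lost from the CTX analysis.

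The cost is wording and one checklist line, with possibly a few more screen failures depending on how the sponsor resolves the conflict. No new data collection is needed.

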#### **5.5 Analysis of compliance**

At every visit, starting with visit V2, the dispensed and returned investigated product is counted, and the patient compliance is assessed. The investigator or his/her authorized representative will count the number of dispensed and returned tablets and document it in the accountability form and CRF. Additionally, date of the first and last product administration, and deviations in the product dosing regimen within the last intervisit interval (if any) will be documented in CRF.

In case of low patient compliance with the investigated treatment (the patient took <80 tablets within the intervisit interval), the patient will be withdrawn from the study.

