
Comparative product.
 
Dose, method of administration
	
Bisoprolol, film-coated tablets
 
One tablet contains bisoprolol hemifumarate and bisoprolol fumarate (2: 1) as active substances 5 mg, and the following excipients: calcium hydrogen phosphate anhydrous - 132 mg; corn starch fine powder - 14.5 mg; colloidal anhydrous silica - 1.5 mg; MCC - 10 mg; crospovidone - 5.5 mg; magnesium stearate - 1.5 mg
 
film coating: hypromellose 2910/15 - 2.2 mg; macrogol 400 - 0.53 mg; dimethicone 100 - 0.11 mg; iron oxide yellow dye (E172) - 0.02 mg; titanium dioxide (E171) - 0.97 mg.
 
Bisoprolol is taken orally, once a day, regardless of meals.          Bisoprolol 5 mg is prescribed to postmenopausal patients with hypertension and osteopenia. Subsequently, in patients with no response, the daily dose is titrated up to 7.5 mg every 2 weeks; then perindopril 10 mg may be added to the regimen at week 8, if necessary. In case of intolerance to perindopril, losartan at a dose of 50 mg/day will be administered.

Other agents allowed by the protocol
	
Losartan film-coated tablets produced by Berlin-Chemie, Germany.
 
Each tablet contains 50 mg of losartan.
 
Losartan is taken orally, once a day, regardless of meals. The product is prescribed to postmenopausal patients with hypertension and osteopenia non-responsive to moxonidine or bisoprolol monotherapy for 4 weeks and intolerant to perindopril.
 
Calcium carbonate + cholecalciferol, chewable tablets          Each tablet contains the following active ingredients calcium carbonate 1250 mg (equivalent to 500 mg of elemental calcium), cholecalciferol (vitamin D3) 5 mcg (200 IU) (as cholecalciferol concentrate - 2 mg).
 
excipients: sorbitol - 390 mg; isomalt - 62 mg; povidone - 36.4 mg; magnesium stearate - 6 mg; aspartame - 1 mg; orange oil - 0.97 mg; mono- and diacylglycerols - 0.0008 mg.
 
The product is taken orally during meals, it should be chewed or dissolve in the mouth.

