### **Treatment regimens**

- **Group 1** patients receive moxonidine with dose titration up to the maximum, then a patient may be switched to the combination therapy, if necessary (step 2 - adding an ACE inhibitor).
- **Group 2** patients receive bisoprolol with dose titration up to the maximum, then a patient may be switched to the combination therapy, if necessary (step 2 - adding an ACE inhibitor).

The investigator will provide a Group 1 patient with moxonidine 0.4 mg in the amount required for 56 days of treatment plus 7 extra days and additionally moxonidine 0.2 mg in an amount required for 42 days of treatment if the dose is titrated up to 0.6 mg/day.

The patient will take the first moxonidine tablet immediately during the visit after all the visit procedures are completed. The patient will be instructed to take 1 tablet of moxonidine 0.4 mg in the morning, daily. The next visit will be scheduled in week 8 after the enrollment visit (in 56 days  $\pm$  5 days after the enrollment visit).

The patient will be asked to bring all the blisters of investigated product (empty, started and not started blisters) to every visit after the study initiation.

The investigator will give the patient blood pressure self-monitoring diary which is to be used by the patient to daily document her BP values and to bring it to every subsequent visit.

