#### 3.8.2 Comparative product

**Name:** Cardioselective beta1 blocker. INN: Bisoprolol.

Produced by Merck KGaA, Germany

**Pharmaceutical form:** film-coated tablets.

One tablet contains bisoprolol hemifumarate and bisoprolol fumarate (2: 1) as active substances 5 mg, and the following excipients: calcium hydrogen phosphate anhydrous - 132 mg; corn starch fine powder - 14.5 mg; colloidal anhydrous silica - 1.5 mg; MCC - 10 mg; crospovidone - 5.5 mg; magnesium stearate - 0.97 mg, film coating: hypromellose 2910/15 - 2.2 mg; macrogol 400 - 0.53 mg; dimethicone 100 - 0.11 mg; iron oxide yellow dye (E172) - 0.02 mg; titanium dioxide (E171) - 0.97 mg.

**Posology and method of administration:** Bisoprolol is taken orally, once a day, regardless of meals.

**Duration of treatment:** Bisoprolol 5 mg is prescribed to postmenopausal patients with hypertension and osteopenia. Subsequently, in patients with no response, the daily dose is titrated up to 7.5 mg every 2 weeks; then perindopril 10 mg may be added to the regimen at week 8, if necessary. Patients should take the medication until study week 48 (V4).

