On 2nd week telephone visit, the investigator evaluates efficacy, safety and tolerability of the investigated treatment. Patients will continue taking moxonidine 0.4 mg QD until next visit V2. If BP control is insufficient, the investigator may increase moxonidine dose to 0.6 mg QD.

On 4th week telephone visit, the investigator evaluates efficacy, safety and tolerability of the investigated treatment. Patients will continue taking moxonidine 0.4 mg (0.6 mg) QD until next visit V2. If BP control is insufficient with moxonidine 0.6 mg QD, the investigator adds perindopril 10 mg QD.

**All group 2 patients** are prescribed with bisoprolol 5 mg monotherapy. At the **V1 enrollment visit**, the patient will be given the medication and will take first dose of bisoprolol in the presence of the investigator. Thereafter, patients will take the medication every morning, during the entire study. The medication will be dispensed to a patient at visits V1, V2, V3, and the patient will start taking the drug on her own on the day following the visit. One tablet of the investigated product should be taken daily, in the morning, regardless of meals.

On 2nd week telephone visit, the investigator evaluates efficacy, safety and tolerability of the investigated treatment. Patients will continue to take bisoprolol 5 mg until visit V2. If BP control is insufficient, the investigator will increase bisoprolol dose to 7.5 mg QD.

On 4th week telephone visit, the investigator evaluates efficacy, safety and tolerability of the investigated treatment. Patients will continue to take bisoprolol 5 mg (7.5 mg) until next visit V2. If BP control is insufficient with bisoprolol 7.5 mg QD, the investigator adds perindopril 10 mg QD.

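### Section 5.5 sets the compliance cut-off at 80 tablets where 4.5 says 80%, and 5.1 conflicts with 3.6.4/3.6.5 on raised blood pressure at V2 and V3

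*Combined protocol and SAP*

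**What the plan says.** **Compliance.** Section 5.5 counts tablets at every visit from V2 and states: "the patient took <80 tablets within the intervisit interval), the patient will be withdrawn from the study". Section 4.5 lists "Low treatment compliance (<80" per cent) among the reasons for which a patient *may* be withdrawn. The two differ in unit (tablets against per cent) and in force (*will* against *may*).

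**Dosing and supply.** Section 5.1 says, for each arm: "One tablet of the investigated product should be taken daily, in the morning, regardless of meals". At V1, section 3.6.2 dispenses the 0.4 mg moxonidine tablets "in the amount required for 56 days of treatment plus 7 extra days". To cover a possible increase to 0.6 mg, the same section supplies "additionally moxonidine 0.2 mg in an amount required for 42 days of treatment". For the comparator, 3.8.2 describes one strength only: "One tablet contains bisoprolol hemifumarate and bisoprolol fumarate (2: 1) as active substances 5 mg".

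**Raised blood pressure at V2 and V3.** Sections 3.6.4 and 3.6.5 titrate when the target (<140/90 mmHg) is not reached, and the schedule in 3.4 marks dose titration at both visits. Section 5.1 treats any reading below 180/120 at those visits as a response and leaves the regimen unchanged; at or above 180/120 the patient is withdrawn.

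**Perindopril timing.** Sections 3.6.3 and 5.1 add it at the week-4 telephone visit. Sections 3.1 and 3.8.1 to 3.8.3 place it at week 8.

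**Prohibited drugs.** Section 5.4.2 bars "Other antihypertensive drugs, except for the investigated products. The only exception is short-acting antihypertensives prescribed by the investigator". It does not mention step-2 perindopril or losartan.

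**The concern.** A withdrawal threshold that a perfectly adherent patient cannot meet is wrong as written, whatever was meant. It matters here because sections 6 and 10.3 analyse efficacy in patients who completed according to the protocol, and 5.5 is one of the rules that decide who completes. Taken literally, retention at V2 would depend on how many tablets make up the prescribed dose, not on adherence.

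The blood-pressure conflict does not need a literal-minded reader. Two sections give a site different instructions for the same patient at the same visit, and the perindopril step has two start times. Which section a site follows would affect who receives add-on treatment and when, and so the secondary endpoint of reaching <140/90 at weeks 8, 24 and 48.

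**Working it through.** **Inputs.** V2, V3 and V4 fall at days 56, 168 and 336, each ± 5 days (3.6.2, 3.6.4, 3.6.5). One tablet a day at the starting dose (5.1). Cut-off of 80 tablets per interval (5.5); 80% (4.5).

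**Interval lengths.**
- V1–V2: 56 days (51 to 61).
- V2–V3: 168 − 56 = 112 days (163 − 61 = 102 to 173 − 51 = 122).
- V3–V4: 336 − 168 = 168 days (331 − 173 = 158 to 341 − 163 = 178).

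**The 80-tablet cut-off against scheduled doses, one tablet a day.** Implied compliance = 80 / scheduled tablets; a true 80% rule needs 0.8 × scheduled tablets, rounded up.

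| Interval | Scheduled tablets | 80 tablets as % of scheduled | Tablets needed for 80% (nominal) |
|---|---|---|---|
| V1–V2 | 56 (51–61) | 143% (131–157%) | 44.8, so 45 |
| V2–V3 | 112 (102–122) | 71% (66–78%) | 89.6, so 90 |
| V3–V4 | 168 (158–178) | 48% (45–51%) | 134.4, so 135 |

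Counting the doses on both end days adds one tablet to V1–V2 (52 to 62) and changes nothing. The supply agrees: an untitrated moxonidine patient receives 56 + 7 = 63 tablets of 0.4 mg at V1 and could not take 80. At one tablet a day, 80 tablets equals 80% only over 80 / 0.8 = 100 days, and no interval in the plan has that length.

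**Fully adherent patients raised at week 2, the time that 3.6.3 and 5.1 give for the dose increase.**
- Moxonidine 0.4 + 0.2 mg: 14 + 2 × 42 = 98 by day 56. At day 51, 14 + 2 × 37 = 88. At day 61, 61 + 42 = 103, since only 42 of the 0.2 mg tablets are dispensed. Always above 80.
- Bisoprolol 7.5 mg: the documents do not say how this dose is made up from a 5 mg tablet. Assuming 1.5 tablets a day, 14 + 1.5 × 42 = 77 (69.5 at day 51, 84.5 at day 61). Assuming two tablets a day, 14 + 2 × 42 = 98.

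**Blood pressure at V2 or V3, side by side.**

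| Reading | 3.6.4 / 3.6.5 | 5.1 | Label in 10.3 |
|---|---|---|---|
| <140/90 | continue | continue | responder |
| not <140/90, but <180/120 | titrate | continue, as a responder | non-responder |
| ≥180/120 | titrate | withdraw | non-responder |

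The middle row is the main conflict. It applies to patients with a step left. Such patients are foreseeable at V2: 3.6.3 makes the week-2 increase discretionary, and under 3.1 and 3.8.1–3.8.3 perindopril starts at week 8, which is V2 itself.

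**The case against.** The strongest reply is that the tablet count is an obvious slip. Section 5.5 is about low compliance, 4.5 gives the matching percentage, and the V1 supply makes 80 tablets impossible for an untitrated moxonidine patient. A site would probably notice. That stands, and it limits the point to an error in a stated rule, with no demonstrated effect on the data.

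Four stronger readings are tempting, and the documents do not support them.

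- *The primary CTX comparison is compromised.* This would need sites to apply the literal count, and no number of affected patients can be derived. A patient withdrawn at V2 leaves the completer population whether or not she has a later sample. For the ITT set, which needs V3 or V4 data, 4.6 asks withdrawn patients to complete final-visit procedures if possible, and those include CTX.
- *The rule withdraws bisoprolol patients and keeps moxonidine patients.* The contrast of 77 against 98 tablets at day 56 rests on assuming 1.5 bisoprolol tablets; with two tablets it disappears.
- *Poor adherence goes unchecked after V2.* The separate <80% ground in 4.5 still covers those intervals, although it is permissive.
- *Step-2 drugs trigger withdrawal under 5.4.2.* The intent to allow them is plain: the synopsis lists losartan under "Other agents allowed by the protocol", and 3.1, 3.6.3, 3.8.3 and 5.1 prescribe perindopril. Only an exemption phrase is missing.

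On blood pressure, it is fair to say that the schedule in 3.4 and sections 3.1, 3.6.4, 3.6.5 and 3.8.3 favour titration, leaving the V2/V3 text in 5.1 as the outlier. A patient already raised at week 2 and given perindopril at week 4 has no further step, so the conflict does not reach her. The endpoint affected is secondary, in an exploratory trial that reports efficacy descriptively. The contradiction remains for patients with a step left.

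**Conclusion.** Both rules are wrong as written and should be corrected.

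1. The threshold in 5.5 contradicts 4.5. Read literally, it removes every fully adherent one-tablet-a-day patient at V2 (51 to 61 tablets against 80), and it corresponds to about 71% and 48% compliance in the next two intervals. This rests only on the visit windows and the daily dose. It is very likely a unit slip, and no effect on the CTX comparison can be counted. The difference between *may* and *will* is a separate inconsistency that correcting the unit would not remove.
2. For readings not below 140/90 but below 180/120 at V2 or V3, with a step still available, the plan gives two opposite instructions, and perindopril starts at week 4 or week 8 depending on the section. This can affect add-on use and the secondary responder results: at V2 through the perindopril timing, and at V3 and V4 through both conflicts. The documents do not allow the number of patients to be estimated.

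The gap in 5.4.2 is minor.

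**What to change.** - **5.5:** replace the tablet count with *less than 80% of the tablets scheduled for that interval at the prescribed dose*. Choose *may* or *will* be withdrawn and use it in both 4.5 and 5.5.
- **5.1, V2 and V3:** state that blood pressure not below 140/90 leads to the next available step, and that 180/120 or above leads to withdrawal. Align 3.6.4 and 3.6.5 with this.
- **Perindopril:** choose week 4 or week 8 and carry it through the synopsis, 3.1, 3.6.3, 3.8.1–3.8.3 and 5.1.
- **5.4.2:** add perindopril or losartan given as protocol step 2 to the exceptions.

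The cost is wording changes and a notice to sites. No visits, procedures or patients are added.
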